7.1.2 Qualitative Research Interviews

Qualitative interviews will be performed for consenting patients at some point between six weeks and three months following registration. Patients and carers chosen for interview will be contacted directly by telephone by the Qualitative Research Team based at Sheffield to arrange a suitable time for the interview. The participant will be given the option of having a telephone interview, being interviewed at home, or being interviewed at the site, which ever option is most convenient for them.

Interviews will also be held with clinical staff, these will be organised by the Qualitative Research Team based at Sheffield on a mutually convenient date.

See Section 10 for more information.

7.1.3 Patient Death

As soon as possible following notification that a patient has died a Death Form should be completed and returned to the Trial Office. Every effort should be made to obtain the date and cause of death and the location of the patient at the time of death.

A clinical records review will be performed to determine what interventions the patient received and what specialists were seen during the month leading up to death. This data will be captured on the CRF.

The site's research team will contact consenting carers to ask them to complete the CODE™ questionnaire approximately three months post-bereavement. The carer will be instructed to return questionnaire to the Trial Office using the pre-paid envelope provided.

7.2 Randomised Controlled Trial

Patients entered into the RCT will be randomised to one of three groups:

- Arm A: Standard Care
- Arm B1: Early referral to SPC using Sites Standard SPC
- Arm B2: Early referral to SPC using Sites Standard SPC + SPARC

7.2.1 Description of Arms

7.2.1.1 Standard Care

Patients randomised to Standard Care will not receive any intervention and should be treated in accordance with the sites standard care pathway.

7.2.1.2 Early Referral to Special Palliative Care using Sites Standard Procedure

Patients randomised to early referral should immediately be referred to local SPC services as well as receiving standard oncology and/or respiratory medicine and follow-up.

Patients in Arm B1 should receive SPC in accordance with the sites usual process.

7.2.1.3 Early Referral to Special Palliative Care Using Sites Standard Procedure and Sheffield Profile for Assessment and Referral for Care (SPARC)

Patients in Arm B2 will receive the same intervention as those in Arm B1 and in addition should receive a HNA using SPARC (see Appendix 2) at the time points specified in the patient visit schedule. A copy of the patient's first SPARC form should be enclosed with the referral letter (see Section Appendix 2). The original form should be sent to the Trial Office and a copy filed in the ISF. Ideally the SPARC assessment form should be completed before any of the other trial questionnaires.

7.2.2 Randomised Controlled Trial Assessment Schedule

The patient visit schedule is summarised in Table 2.

Table 2: Patient Visit Schedule - Randomised Controlled Trial

Assessment		Follow-up Period	On-going Follow-up	After Death
		Monthly, or to coincide with treatment schedule for 6 months	2-monthly for 6 months then 3 monthly until death or further two years	
Eligibility check	X			
ECOG Performance Status	X	X	X	
Patient's Informed Consent	X			
Carer's Informed Consent (once patient has consented)	Х			
Modified Glasgow Prognosis Score (mGPS)	Х	X*		
Patient Randomisation	Х			
Demography, medical history	Х			
Concomitant medication	Х	Х	Х	
Scottish lung cancer co-morbidity index	Х			
Patient Questionnaire Booklet (randomisation and time-point specific)	Х	X	X	
Patient diary collected		X	X	
Sheffield Profile for Assessment and Referral for Care (SPARC) ONLY IF RANDOMISED TO ARM B2 [†]	Х	X	X	
Montreal Cognitive Assessment scale (MoCA) (consenting participants only)	Х	X *		
Carer Questionnaire Booklet	Х	X	X	
Qualitative Interviews (consenting participants only)		X [‡]		
Recording of resource use		X	X	
Treatment details and measurement of response (as per local practice)		X	X	
Relapse/Progression		X	Х	
Notification of death, location of death				Х
Clinical Records Review: Interventions and Specialists seen during month leading up to death				Х
CODE™ (consenting participating carers only; 2-3 months post-bereavement)				Х

Notes

Page | 16 of 64

^{*} mGPS & MoCA will be measured at 3 and 6 months during follow-up (see Section 7.3)

[‡] Performed at approximately 3 and 6 months from trial entry

[†] A copy of SPARC should be provided to the patient's palliative care team after each assessment, the original should be returned to the Trial Office and a copy retained in the ISF

7.2.2.1 Baseline Assessments

Baseline assessments must be within two to four weeks of the patient being diagnosed and as soon as possible after entry into the trial. The following assessments should be performed and will be captured on the Baseline Form:

- mGPS* (see Appendix 3 and Section 7.3)
- Demographics
- Medical history
- Scottish Lung Cancer Co-morbidity Index Score (see Appendix 5, for list of co-morbidities and scores)
- Current concomitant medications
- ECOG (as per eligibility assessment; see section 4.1 and Appendix 6)
- An assessment of cognitive function should also be made using MoCA (see Appendix 4) for those patients who consented to the use of this optional measure

The patient should be asked to complete the:

- SPARC questionnaire (if randomised to Arm B2 only)[†]
- Baseline Patient Questionnaire Booklet

The carer should also be given the Carer Questionnaire Booklet (if they have agreed to participate).

Prior to completing the questionnaire a member of the site research team should discuss the questionnaires with the patient, and if applicable the carer, and answer any questions they may have. Once the questionnaires have been completed by the patient/carer the site research team should check to make sure that all of the questions have been completed and that in particular that the date the questionnaires are completed has been accurately recorded.

The patient should also be given the Patient Diary (this will have sufficient diary sheets to last for 6 months). Completion of the diary should be explained to them and they should be asked to return completed sheets at their next appointment. A larger format version of the diary is available (A4, larger font size) for patients who require large print. Completed Patient Diary sheets will be collected at the next clinic visit.

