7.2.2.2 Follow-up Assessments

The patient should be followed up at least once per month for six months. Patients being treated every third week (for example those receiving chemotherapy) will be seen every three weeks while on treatment. The patient's visits should be organised to correspond with their treatment visits where possible.

The following should be assessed at each visit (be that three weekly of four weekly):

- Disease status
- ECOG status (see Appendix 6)

Page | 17 of 64 Version 1.0a, 8 Apr 2016

^{*} Please note: mGPS must be performed prior to randomisation, as this is required to assess eligibility.

Please note: A copy of SPARC should be sent to the patient's palliative care team with the referral letter, the original should be returned to the Trial Office and a copy retained in the ISF

Concomitant medication review

The patient should be asked to complete the following during the clinic appointment:

- Appropriate Follow-up Patient Questionnaire Booklet
- SPARC questionnaire (only if randomised to Arm B2)

In addition to the above, at three and six month assessments, the following must also be assessed:

- mGPS (see Appendix 3 and Section 7.3)
- MoCA (see Appendix 4)

The carer should be asked to complete the Carer Questionnaire Booklet *.

* Please note: If the trial registered carer is not accompanying the patient, please send the carer questionnaire booklet home with patient so that the carer may complete and return it to the site research team at the next follow-up clinic visit.

Completed questionnaires booklets and forms should be returned to the Trial Office with the patient's completed diary sheets.

Please note: The patient may require a new Patient Diary after their six month assessment visit.

The following information will be collected on the CRF at all follow-up visits:

- Treatment details
- Response to treatment (as per local practice)
- Details of relapse/progression
- Hospital admissions, including duration and reason for admission
- · Details of patient referral to the SPC team
- Resource use (see Appendix 1 for list of medical interventions)

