19.2.2.2 Secondary Outcome Measures

The following measures will be reported by treatment arm:

Overall survival: A Kaplan Meier plot of overall survival will be reported along with hazard ratio and median survival (both with 95% CI).

Anxiety/depression: The average change in HADS score from baseline to six months will be compared using a t-test (or non-parametric alternative). The mean area under curve will also be compared using a t-test.

Pain: The average change in pain domain score from baseline to six months will be compared using a t-test (or non-parametric alternative). The mean area under curve will also be compared using a t-test.

Cost Effectiveness:

- Days spent in hospital/hospice Mean (95% CI) stay and overall stay duration and frequency
 of hospital/hospice say durations will be compared using a t-test (or non-parametric alternative).
 The number of patients admitted but not discharged will be reported. The proportion of patients
 spending time in hospital/hospice will be reported.
- Use, or not, of medical interventions in last month of life A line-listing of medical interventions including, where applicable, intervention type, dose, duration and other pertinent metrics. The period over which these interventions are to be observed will also be reported (some may not have been followed for a month).

ITU admission: The number of ITU visits, and the number of patients making those visits along with the mean (95% CI) length of each visit, and the mean (95% CI) of patients overall ITU duration.

Use of CPR: The proportion of patients requiring CPR and the average number of resuscitations required per patient will be reported.

For each of the questionnaire based outcome measures the mean (sd) score will be reported by visit.

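### RCT baseline questionnaires are completed after allocation is known, which can bias the HADS and pain change scores; the SPARC order in Arm B2 is also left unsettled

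*Protocol*

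**What the plan says.** **Timing of baseline.** Protocol Section 7.2.2.1 states: "Baseline assessments must be within two to four weeks of the patient being diagnosed and as soon as possible after entry into the trial". Section 6 (Trial Entry) covers RCT entry under randomisation, and Section 6.2 issues the trial number there. The baseline list includes "SPARC questionnaire (if randomised to Arm B2 only"), so that session has to follow both randomisations. A footnote to the same list says "mGPS must be performed prior to randomisation, as this is required to assess eligibility". ECOG is carried over from the eligibility check. No comparable rule covers the questionnaire booklet. Section 3.2 describes the RCT as non-blinded, and Section 7.2.1.2 adds: "Patients randomised to early referral should immediately be referred to local SPC services".

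**Use of baseline.** Section 19.2.2.2 says: "The average change in HADS score from baseline to six months will be compared using a t-test" (or a non-parametric alternative), and plans the same comparison for pain. Section 19.2.2.1 compares GHSS at three months by t-test, with no baseline term. QAS is an area under the EQ-5D-5L utility curve over six months (Section 19.2.1.1).

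**Order of questionnaires.** For Arm B2, Section 7.2.1.3 says: "Ideally the SPARC assessment form should be completed before any of the other trial questionnaires". The bulleted lists do not agree on order. Sections 7.2.2.1 (baseline) and 7.2.2.3 (long term) name SPARC before the booklet; Section 7.2.2.2 (follow-up, which covers the three-month visit) names the booklet before SPARC.

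**Booklet content.** Table 2 has the row "Patient Questionnaire Booklet (randomisation and time-point specific"). Table 3 in Appendix 8 shows a single RCT baseline booklet for all arms, with SPARC listed outside it.

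**The concern.** A baseline should be taken before anything that depends on the arm can influence it. Here, patients answer self-report questions after learning whether they are being sent to palliative care, and nobody is blinded. Any reaction to that news is recorded as part of baseline and then subtracted in a change score.

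The consequence is concrete because Section 2.1.1 asks what harms earlier referral might cause and gives patient anxiety as its example. HADS is the instrument for anxiety, and Appendix 8 schedules it only at baseline, three months and six months. An immediate rise in anxiety caused by the referral could therefore sit in the baseline value and be removed from the comparison meant to detect it.

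The second issue is the order of forms. SPARC has 45 items, many on distress, including pain, anxiety, low mood and worries about dying. If only Arm B2 answers these just before the outcome questionnaires, its answers may shift for reasons unrelated to care.

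**Working it through.** **1. The plan's own figures.** With a difference of 7 and an SD of 23 (Section 19.2.5.1), two-sided 5% and 80% power, the normal approximation gives 340 analysed (t-based 341), and 340/0.65 rounds up to 524 randomised. The protocol has 342 and 525. For QAS (difference 0.5, SD 2) it gives 504 against 506. These reproduce closely, and nothing below changes them.

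**2. Baseline timing and change scores.** Let allocation knowledge shift reported baseline by d in Arm B only.
- Change in Arm B = (follow-up) − (baseline + d), so the A v B contrast moves by −d, the full shift with opposite sign.
- Suppose referral raises anxiety by a at once. If the rise persists to six months, the contrast shows a − a = 0 and the harm disappears. If it has faded, the contrast shows 0 − a = −a, which reads as a benefit.
- The documents give no value for d or a, nor a direction.

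**3. Baseline timing and areas under the curve.** Trapezoids are assumed.
- HADS at 0, 3 and 6 months: baseline weight = 1.5/6 = 25% of the area.
- QAS with monthly visits: baseline weight = 0.5 month. For an assumed utility shift of 0.02 to 0.04, bias = 0.5 × 0.02 = 0.01 to 0.5 × 0.04 = 0.02 quality-adjusted months. Against the 0.5-month target, this is 2 to 4%.
- A genuine early reaction is part of the effect in an area measured from randomisation; only a reporting shift is bias.

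**4. Baseline timing and GHSS.** The outlined test compares three-month values only. The baseline weight is zero.

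**5. SPARC order.** Let answering SPARC first shift B2 scores by s at that sitting. Allocation is 1:1 for A:B and 1:1 for B1:B2 (Section 6.2).
- B1 v B2 moves by s; A v B moves by s/2.
- In a change score, an equal s at both visits cancels. If SPARC comes first at baseline and second at follow-up, as the lists in 7.2.2.1 and 7.2.2.2 would suggest, it does not cancel.

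Illustration for three-month GHSS, with s assumed: 171 per arm (342/2), SD 23, standard error 23 × √(2/171) = 2.49; for B1 v B2, about 85.5 each, standard error 23 × √(2/85.5) = 3.52.

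| Assumed s (points) | A v B: rejection with no true effect | B1 v B2: rejection with no true effect | A v B: power for a true 7 if s lowers B2 |
|---|---|---|---|
| 0 | 5.0% | 5.0% | 80% |
| 1 | 5.5% | 5.9% | 74% |
| 2 | 6.9% | 8.8% | 67% |
| 5 | 17.1% | 29.5% | 44% |

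These rows show sensitivity only. They are not estimates.

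**The case against.** **SPARC first is advisory.** The sentence in Section 7.2.1.3 says only that this is ideal. It closes a paragraph about the first SPARC form and the referral letter, and the list governing the three-month visit names the booklet first. This stands as a limit: an order effect at three months is possible but not prescribed. The sentence is not confined to baseline, however, and the lists point different ways, so sites may differ.

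**SPARC is part of the B2 intervention.** Its effect through better-directed care is treatment effect. This stands; only the same-sitting effect on answers is measurement bias.

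**Referral is not receipt of care.** For B2, a copy of SPARC goes with the referral letter, so referral need not precede the baseline session; for B1, being referred is not yet being seen. This also stands, but the argument rests on knowing one's allocation, which has happened in either case.

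**Stronger readings that the text does not support.**
- A reader might infer that a contaminated baseline biases the GHSS co-primary. The outlined test has no baseline term, and the protocol describes no baseline-adjusted GHSS model.
- A reader might infer from the Table 2 label that arms receive different baseline booklets. Table 3 shows the same contents for all; the label needs reconciling but proves no difference.
- A reader might infer that SPARC priming necessarily biases change scores. It cancels if the order and its effect are the same at both visits.

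**Conclusion.** The point holds in a limited form. As written, the RCT baseline booklet follows allocation in a non-blinded trial, and this can bias the HADS and pain change-from-baseline comparisons by the whole of any arm-specific reporting shift. It can also absorb an early anxiety effect of referral. The effect on QAS is small (2 to 4% of the target difference under the assumed utility shift, monthly visits and trapezoids), and the outlined three-month GHSS comparison is not directly affected.

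The order of SPARC and the booklet in Arm B2 is a separate, possible source of bias. It would reach three-month GHSS only if sites apply the advisory sentence at follow-up, and then in full for B1 v B2 and by half for A v B. The documents fix neither direction nor size.

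No stated figure is wrong. This is an inexpensive improvement rather than a flaw that undermines the primary analysis, but it has to be made before recruitment: a baseline already collected after allocation cannot be retaken.

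**What to change.** 1. In Sections 6.2 and 7.2.2.1 and in Table 2, require the Baseline Patient Questionnaire Booklet (and MoCA where consented) after consent and before the randomisation call. Record its completion date on the Randomisation Form.
2. In Section 7.2.1.3, state that the outcome booklet is completed before SPARC at every visit, and align the lists in 7.2.2.1 to 7.2.2.3. SPARC can still accompany the referral letter.
3. Reconcile the Table 2 description of the booklet as specific to randomisation with Table 3.

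**Cost.** Protocol wording and one extra item on the Randomisation Form. Randomisation waits roughly 20 minutes, from the Appendix 8 completion times (about 15 for EQ-5D-5L with the EORTC modules, plus 5 for HADS), and about 10 more where MoCA is done (Appendix 4). A few patients may complete a booklet and then not be randomised. Sample size does not change.

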7.2.2.2 Follow-up Assessments

The patient should be followed up at least once per month for six months. Patients being treated every third week (for example those receiving chemotherapy) will be seen every three weeks while on treatment. The patient's visits should be organised to correspond with their treatment visits where possible.

The following should be assessed at each visit (be that three weekly of four weekly):

- Disease status
- ECOG status (see Appendix 6)

Page | 17 of 64 Version 1.0a, 8 Apr 2016

^{*} Please note: mGPS must be performed prior to randomisation, as this is required to assess eligibility.

Please note: A copy of SPARC should be sent to the patient's palliative care team with the referral letter, the original should be returned to the Trial Office and a copy retained in the ISF

Concomitant medication review

The patient should be asked to complete the following during the clinic appointment:

- Appropriate Follow-up Patient Questionnaire Booklet
- SPARC questionnaire (only if randomised to Arm B2)

In addition to the above, at three and six month assessments, the following must also be assessed:

- mGPS (see Appendix 3 and Section 7.3)
- MoCA (see Appendix 4)

The carer should be asked to complete the Carer Questionnaire Booklet *.

* Please note: If the trial registered carer is not accompanying the patient, please send the carer questionnaire booklet home with patient so that the carer may complete and return it to the site research team at the next follow-up clinic visit.

Completed questionnaires booklets and forms should be returned to the Trial Office with the patient's completed diary sheets.

Please note: The patient may require a new Patient Diary after their six month assessment visit.

The following information will be collected on the CRF at all follow-up visits:

- Treatment details
- Response to treatment (as per local practice)
- Details of relapse/progression
- Hospital admissions, including duration and reason for admission
- · Details of patient referral to the SPC team
- Resource use (see Appendix 1 for list of medical interventions)

7.2.2.3 Long Term Follow-up Assessments

After the six month follow-up visit RCT patients will be followed up every two months for a further six months. Thereafter patients will be followed up three monthly until death or for a maximum of two years.

The patient should be asked to complete:

- SPARC questionnaire (only if randomised to Arm B2)
- Long Term Follow-up Patient Questionnaire Booklet

Page | 18 of 64 Version 1.0a, 8 Apr 2016

Please note: A copy of SPARC should be provided to the patient's palliative care team after each assessment, the original should be returned to the Trial Office and a copy retained in the ISF

Please note: A copy of SPARC should be provided to the patient's palliative care team after each assessment, the original should be returned to the Trial Office and a copy retained in the ISF

The carer should be asked to complete the Carer Questionnaire Booklet*.

Completed questionnaires should be returned to the Trial Office with the patient's completed diary sheets.

*Please note: If the trial registered carer is not accompanying the patient, please send the carer questionnaire booklet home with patient so that the carer may complete and return it to the site research team at the next follow-up clinic visit.

Survival data, including information on relapse and progression and on-going resource use will be collected on the CRF. If the patient receives additional treatment for relapse/progression they should resume monthly assessments (see Section 7.2.2.2).

7.2.3 Qualitative Research Interviews

Qualitative interviews will be performed for selected consenting patients and carers at approximately three and six months after randomisation. Patients/carers chosen for interview will be contacted directly by telephone by the Qualitative Research Team based at Sheffield to arrange a suitable time for the interview. The patient/carer will be given the option of having a telephone interview, being interviewed at home, or being interviewed at the site, which ever option is most convenient for them.

Interviews will also be held with clinical staff, these will be organised by the Qualitative Research Team based at Sheffield on a mutually convenient date.

See Section 10 for more information.

7.2.4 Patient Death

As soon as possible following notification that a patient has died a Death Form should be completed and returned to the Trial Office. Every effort should be made to obtain the date and cause of death and the location of the patient at the time of death.

A clinical records review will be performed to determine what medical interventions (see Appendix 1) the patient received and what specialists were seen during the month leading up to death. This data will be captured on the CRF.

The site's research team will contact consenting carers approximately three months post-bereavement to ask whether they would complete the CODE™ questionnaire. The carer will be instructed to return questionnaire to the Trial Office using the pre-paid envelope provided.

